9.8 Timing of Event Reporting

- UADEs must be reported within 10 working days to the FDA after the sponsor first receives notice of the adverse effect.
- Other reportable adverse events, device malfunctions (with or without an adverse event) and device complaints should be reported promptly, but there is no formal required reporting period.
- The IDE Sponsor will investigate the UADE and if indicated, report the results of the investigation to the IRBs and FDA, within 10 working days of the study team becoming aware of the UADE per 21CFR 812.46(b) (2).
- In the case of a device system component malfunction (e.g. pump, CGM, control algorithm), information will be forwarded to the responsible manufacturer by the study personnel.

9.9 Stopping Criteria

9.9.1 Participant Discontinuation

Rules for discontinuing study device use are described below.

- The investigator believes it is unsafe for the participant to continue on the intervention. This could be due to the development of a new medical condition or worsening of an existing condition; or participant behavior contrary to the indications for use of the device that imposes on the participant's safety
- The participant requests that the treatment be stopped
- Two distinct episodes of DKA
- Two distinct severe hypoglycemia events as defined in section 9.2.1.

9.9.2 Suspending/Stopping Overall Study

In the case of an unanticipated system malfunction resulting in a severe hypoglycemia or severe hyperglycemia event (as defined in section 9.2), use of the study device system will be suspended while the problem is diagnosed.

CLINICAL PROTOCOL

986 In addition, study activities could be similarly suspended if the manufacturer of any constituent
987 study device requires stoppage of device use for safety reasons (e.g. product recall). The affected
988 study activities may resume if the underlying problem can be corrected by a protocol or system
989 modification that will not invalidate the results obtained prior to suspension. Definition of a Data
990 Breach.

991 The study must also stop if there are three severe hypoglycemia events or three DKA events.
992 After further medical/safety review of the events, the study may resume if the events are
993 determined to be unrelated to an unanticipated system malfunction.

994 A data breach is defined in the HITECH Act (43 USC 17932) as an unauthorized acquisition, access,
995 or use of protected health information (PHI) that compromises the security or privacy of such
996 information.

CLINICAL PROTOCOL

997 **Chapter 10: Miscellaneous Considerations**

998 **10.1 Prohibited Medications, Treatments, and Procedures**

999 Participants using non-approved insulins at the time of enrollment will be asked to contact their
1000 personal physician to change their prescribed personal insulin to a rapid-acting insulin approved
1001 for use in the t:slim X2 pump (e.g. lispro or aspart) for the duration of the trial.

1002 The devices (insulin pump, CGM) must be removed before Magnetic Resonance Imaging (MRI),
1003 Computed Tomography (CT) or diathermy treatment. Participants may continue in the trial after
1004 temporarily discontinuing use if requiring one of the treatments above.

1005 **10.2 Participant Withdrawal**

1006 Participation in the study is voluntary. Participant may withdraw at any time. For participants
1007 who do withdraw from the study, the study team will determine if their data will be used in
1008 analysis.

1009 **10.3 Confidentiality**

[figure not shown]
1010 For security and confidentiality purposes, subjects will be assigned an identifier that will be used
1011 instead of their name. Protected health information gathered for this study may be shared with
1012 the third party collaborators. De-identified subject information may also be provided to
1013 collaborators involved in the study after the appropriate research agreement has been executed.

CLINICAL PROTOCOL

1014 Chapter 11: Statistical Consideration

1015 The intent of this pilot-feasibility study is to introduce and initially test elements of two modules
1016 to be included in a future Adaptive Biobehavioral Control (ABC) system: (1) A Behavioral
1017 Adaptation Module (BAM) and (2) An Auto Titration Module (ATM) and a Web Simulation Model
1018 (WST). BAM and ATM / WST will be provided to users of the t:slim X2 with Control-IQ closed-loop
1019 system. The only purpose of this trial is safety testing and receiving feedback from the
1020 participants regarding system functionality and user interface.

1021 11.1 Design and Randomization

1022 The study will recruit current users of the Control-IQ system. Following a 2-week baseline using
1023 Control-IQ only, the participants will be randomized 1:1 to Control-IQ + ATM / WST vs Control IQ
1024 + ATM / WST + BAM and will be followed for 6 weeks. The randomization list will use a sequence
1025 of computer-generated pseudorandom Bernoulli trials. The 6 weeks of active trial will be used
1026 for assessment of the safety and usability of ATM / WST and BAM. The baseline data and the last
1027 2 weeks of the active trial will be used for secondary comparisons of CGM-based metrics of
1028 glycemic control.

1030 11.2 Sample Size

1031 We intend to recruit up to 45 users of Control-IQ, with the objective to randomize N=30 subjects.
1032 The number of participants is a convenience sample not based on statistical principles. This
1033 sample will provide ~180 weeks of data for the assessment of the safety and utility of the ATM
1034 and up to 90 weeks for assessment of the safety and utility of the BAM.

1035 11.3 Outcome Measures

1036 11.3.1 Primary Efficacy Endpoint

1037 Safety assessment of ATM / WST and BAM.

1038 11.3.2 Secondary Outcome

1039 CGM-based metrics and user experience (UX) questionnaires, including:

CLINICAL PROTOCOL

1040 • Percentage of readings in the target ranges of 70-180 and 70-140 mg/dl;
1041 • Mean glucose;
1042 • Glucose variability measured by standard deviation and coefficient of variation;
1043 • Percentage of readings <70, 60, and 54 mg/dl;
1044 • Low blood glucose index (LBGI)¹⁰
1045 • Percentage of readings >180, 250, and 300 mg/dl;
1046 • High blood glucose index (HBGI)¹⁰
1047 • ABC Pilot Pre and Post Study Questionnaire
1048 • INSPIRE

1049 **11.4 Safety Analyses**

1050 All randomized participants will be included in these analyses and the circumstances of all
1051 reportable cases of the following will be summarized and tabulated by treatment group:

1052 • Severe hypoglycemia;
1053 • Diabetic ketoacidosis (DKA);
1054 • Ketone events defined as a calendar day with ketone level >1.0 mmol/L;
1055 • Serious adverse events (SAE) with a possible or greater relationship to a study device
1056 (including anticipated and unanticipated adverse device effects);
1057 • Other serious adverse events not related to a study device, and
1058 • Adverse device effects (ADE) that do not meet criteria for SAE.

1059 Criteria for Success have been discussed with FDA during the submission of our previous pilot
1060 study (IDE G170255, “A Pilot Test of t:slim X2 with Control-IQ Technology”), which was used to
1061 introduce Control-IQ and enable a subsequent pivotal trial. These criteria included system safety
1062 checks and CGM-based performance criteria consistent with the recommendations of the
1063 International Consensus on Time-in-Range. Because these criteria are well established, we will
1064 keep them to gauge the success of the pilot evaluation of the new modules ATM / WST and BAM:

1065 • No critical ATM / WST or BAM errors;
1066 • No SAE or ADE related to the use of ATM / WST or BAM;
1067 • Percent time in the range 70-180 mg/dL: mean 71% \pm 11;
1068 • Percent time <70 mg/dL: median <5%.
1069 • Percent time >250 mg/dL: median <10%.

CLINICAL PROTOCOL

1070 **11.5 Baseline Descriptive Statistics**

1071 Baseline demographic and clinical characteristics of the cohort of all randomized participants will
1072 be summarized in a table using summary statistics appropriate to the distribution of each
1073 variable. Descriptive statistics will be displayed overall and by treatment group, and will include:

- 1074 • Demographics (e.g. age, duration of diabetes, and other);
- 1075 • Baseline HbA1c, and
- 1076 • CGM-based metrics from the 2-week baseline use of Control-IQ:
 - 1077 ○ Percentage of readings in the target ranges of 70-180 and 70-140 mg/dl;
 - 1078 ○ Mean glucose;
 - 1079 ○ Glucose variability measured by standard deviation and coefficient of variation;
 - 1080 ○ Percentage of readings <70, 60, and 54 mg/dl;
 - 1081 ○ Low blood glucose index (LBGI);¹⁰
 - 1082 ○ Percentage of readings >180, 250, and 300 mg/dl;
 - 1083 ○ High blood glucose index (HBGI).¹⁰

1084 **11.6 Device Issues**

1085 The following tabulations and analyses will be performed by treatment group to assess device
1086 issues:

- 1087 • Device malfunctions requiring study team contact and other reported device issues
- 1088 • Sensor performance metrics (difference, absolute relative difference, and International
1089 Organization for Standardization criteria) – if applicable, by sensor version.
- 1090 • % time CGM data available - overall and by month
- 1091 • % time in different operational modes per week - overall and by month

1092 **11.7 Analysis of Secondary CGM-based Outcomes**

1093 The study design includes repeated measures (baseline vs last 2 weeks of study) on all secondary
1094 CGM and UX outcomes (Figure 1); thus, we will use a linear mixed-effect model that corresponds
1095 well to this structure^{5,6} (e.g. Linear Mixed Models in SPSS.⁷), with “Subject” as a random factor
1096 and “Group” as a fixed factor. The models will adjust for age and HbA1c as fixed effects. We
1097 should note that similar results may be generated by repeated measures ANOVA, but mixed
1098 models handle missing data better (e.g. ANOVA only uses listwise deletion, which could reduce
1099 power and introduce bias towards study completers).^{8,9}

1100 The general principles that will be followed during analysis are:

- 1101 • The analysis will follow an Intention-to-treat (ITT) approach;

CLINICAL PROTOCOL

1102 • All randomized participants will be included in the primary safety analysis and in the
1103 secondary analyses of CGM metrics.

1104 • All covariates obtained on a continuous scale will be entered into the models as
1105 continuous variables, unless it is determined that a variable does not have a linear
1106 relationship with the outcome. In such a case, categorization and/or transformation will
1107 be explored. All p-values will be two-sided.

1108 • Standard residual diagnostics will be performed for all analyses. If values are highly
1109 skewed, then an alternate transformation or nonparametric methods will be used.
1110 Previous experience suggests that no transformation or nonparametric analyses will be
1111 necessary for TIR 70-180 mg/dL, TIR above 180 mg/dL, mean glucose, or HbA_{1c}. Other
1112 outcomes, such as TIR below 70 mg/dL are typically skewed.

CLINICAL PROTOCOL

1113 **Chapter 12: Data Collection and Monitoring**

1114 **12.1 Case Report Forms and Device Data**

1115 The study data are collected through a combination of case report forms (electronic and paper)
1116 and electronic device data files obtained from the software and individual hardware
1117 components. These electronic device files and electronic CRFs are considered the primary source
1118 documentation.

1119 When data are directly collected in electronic case report forms, this will be considered the
1120 source data. Records will be maintained in accordance with ICH E6 and institutional regulatory
1121 requirements for the protection of confidentiality of participants.

1122 **12.2 Study Records Retention**

1123 Study documents should be retained for a minimum of 2 years after the last approval of a
1124 marketing application in an ICH region and until there are no pending or contemplated marketing
1125 applications in an ICH region or until at least 2 years have elapsed since the formal
1126 discontinuation of clinical development of the investigational product. These documents should
1127 be retained for a longer period, however, if required by local regulations. No records will be
1128 destroyed without the written consent of the sponsor, if applicable. It is the responsibility of the
1129 sponsor to inform the investigator when these documents no longer need to be retained.

1130 **12.3 Protocol Deviations**

1131 A protocol deviation is any noncompliance with the clinical trial protocol, Good Clinical Practices
1132 (GCP), or procedure requirements. The noncompliance may be either on the part of the
1133 participant, the investigator, or the study site staff. As a result of deviations, corrective actions
1134 may be developed by the site and implemented as appropriate. Major deviations will be reported
1135 to the IRB-HSR within 7 calendar days of when the study team becomes aware of the event.

CLINICAL PROTOCOL

1136 **Chapter 13: Ethics/Protection of Human Participants**

1137 **13.1 Ethics Standard**

1138 The investigator will ensure that this study is conducted in full conformity with Regulations for
1139 the Protection of Human Participants of Research codified in 45 CFR Part 46, 21 CFR Part 50, 21
1140 CFR Part 56, and/or the ICH E6.

1141 **13.2 Institutional Review Boards**

1142 The protocol, informed consent form(s), recruitment materials, and all participant materials will
1143 be submitted to the IRB for review and approval. Approval of both the protocol and the consent
1144 form must be obtained before any participant is enrolled. Any amendment to the protocol will
1145 require review and approval by the IRB before the changes are implemented to the study. All
1146 changes to the consent form will be IRB approved; a determination will be made regarding
1147 whether previously consented participants need to be re-consented.

1148 **13.3 Informed Consent Process**

1149 **13.3.1 Consent Procedures and Documentation**

1150 Informed consent is a process that is initiated prior to an individual's agreement to participate in
1151 the study and continues throughout the individual's study participation. Extensive discussion of
1152 risks and possible benefits of participation will be provided. Consent forms will be IRB approved
1153 and the participant will be asked to read and review the document. The investigator or their
1154 delegate will explain the research study to the participant and answer any questions that may
1155 arise. All participants will receive a verbal explanation in terms suited to their comprehension of
1156 the purposes, procedures, and potential risks of the study and of their rights as research
1157 participants. Participant will have the opportunity to carefully review the written consent form
1158 and ask questions prior to signing.

1159 The participant will sign the informed consent document prior to any procedures being done
1160 specifically for the study. A copy of the informed consent document will be given to the
1161 participant for their records. The rights and welfare of the participants will be protected by
1162 emphasizing to them that the quality of their medical care will not be adversely affected if they
1163 decline to participate in this study.

1164 **13.3.2 Participant and Data Confidentiality**

1165 The study monitor, representatives of the IRB or device company supplying study product may
1166 inspect all documents and records required to be maintained by the investigator, including but
1167 not limited to, medical records (office, clinic, or hospital) for the participants in this study.

CLINICAL PROTOCOL

1168 The study participant's contact information will be securely stored at the clinical site for internal
1169 use during the study. At the end of the study, all records will continue to be kept in a secure
1170 location for as long a period as dictated by local IRB and Institutional regulations.

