826 A device complication or complaint is something that happens to a device or related to device
827 performance, whereas an adverse event happens to a participant. A device complaint may occur

CLINICAL PROTOCOL

828 independently from an AE, or along with an AE. An AE may occur without a device complaint or
829 there may be an AE related to a device complaint. A device malfunction is any failure of a device
830 to meet its performance specifications or otherwise perform as intended. Performance
831 specifications include all claims made in the labeling for the device. The intended performance
832 of a device refers to the intended use for which the device is labeled or marketed. (21 CFR 803.3).

833 **9.2 Reportable Events**

834 For this protocol, a reportable adverse event includes any untoward medical occurrence that
835 meets one of the following criteria:

- 836 • a serious adverse event as defined in section 9.1.2
- 837 • an adverse device effect as defined in section 9.1.4, unless excluded from reporting in
838 section 9.7
- 839 • an adverse event as defined in section 9.1.4 occurring in association with a study
840 procedure
- 841 • an ae as defined in section 9.1.1 which leads to discontinuation of a study device for 2 or
842 more hours
- 843 • hypoglycemia meeting the definition of severe hypoglycemia as defined in section 9.2.1
- 844 • diabetic ketoacidosis (DKA) as defined in section 9.2.2 or in the absence of DKA, a
845 hyperglycemic or ketosis event meeting the criteria defined below
- 846 • hypoglycemia and hyperglycemia not meeting the criteria below will not be recorded as
847 adverse events unless associated with an Adverse Device Effect. Skin reactions from
848 sensor placement are only reportable if severe and/or required treatment.

849 **9.2.1 Hypoglycemia Event**

850 Hypoglycemia not associated with an Adverse Device Effect is only reportable as an adverse event
851 when the following definition for severe hypoglycemia is met:

- 852 • the event required assistance of another person due to altered consciousness, and
853 required another person to actively administer carbohydrate, glucagon, or other
854 resuscitative actions;
- 855 • impaired cognitively to the point that he/she was unable to treat himself/herself, was
856 unable to verbalize his/ her needs, was incoherent, disoriented, and/or combative, or
857 experienced seizure or coma. These episodes may be associated with sufficient

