858 neuroglycopenia to induce seizure or coma;

CLINICAL PROTOCOL

859 • if plasma glucose measurements are not available during such an event, neurological
860 recovery attributable to the restoration of plasma glucose to normal is considered
861 sufficient evidence that the event was induced by a low plasma glucose concentration.

862 **9.2.2 Hyperglycemia Events/Diabetes Ketoacidosis**

863 Hyperglycemia not associated with an Adverse Device Effect is only reportable as an adverse
864 event when one of the following four criteria is met:

865 • the event involved DKA, as defined by the Diabetes Control and Complications Trial
866 (DCCT) and described below
867 • evaluation or treatment was obtained at a health care provider facility for an acute event
868 involving hyperglycemia or ketosis
869 • blood ketone level ≥ 1.5 mmol/L and communication occurred with a health care provider
870 at the time of the event
871 • blood ketone level ≥ 3.0 mmol/L, even if there was no communication with a health care
872 provider

873 Hyperglycemic events are classified as DKA if the following are present:

874 • symptoms such as polyuria, polydipsia, nausea, or vomiting;
875 • serum ketones ≥ 1.5 mmol/l or large/moderate urine ketones;
876 • treatment provided in a health care facility
877 • all reportable Adverse Events—whether volunteered by the participant, discovered by
878 study personnel during questioning, or detected through physical examination,
879 laboratory test, or other means—will be reported on an adverse event form online.

880 **9.3 Relationship of Adverse Event to Study Device**

881 The study investigator will assess the relationship of any adverse event to be related or unrelated
882 by determining if there is a reasonable possibility that the adverse event may have been caused
883 by the study device.

884 To ensure consistency of adverse event causality assessments, investigators should apply the
885 following general guideline when determining whether an adverse event is related:

886 • There is a plausible temporal relationship between the onset of the adverse event and
887 the study intervention, and the adverse event cannot be readily explained by the
888 participant's clinical state, intercurrent illness, or concomitant therapies; and/or the
889 adverse event follows a known pattern of response to the study intervention; and/or the

CLINICAL PROTOCOL

890 adverse event abates or resolves upon discontinuation of the study intervention or dose

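### The only stated condition for resuming after the three-event stop in section 9.9.2 tests for a malfunction, not for relatedness to ATM/WST or BAM

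*Combined protocol and SAP*

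**What the plan says.** Section 9.9.2 (Suspending/Stopping Overall Study) contains two safety rules that matter here.

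- **Malfunction suspension.** It opens "In the case of an unanticipated system malfunction resulting in a severe hypoglycemia or severe" hyperglycemia event, refers to section 9.2 for the definition, and suspends use of the system while the problem is diagnosed.
- **Event-count stop.** "The study must also stop if there are three severe hypoglycemia events or three DKA events". No cause is required. It continues: "After further medical/safety review of the events, the study may resume if the events are" "determined to be unrelated to an unanticipated system malfunction".

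Three other places deal with harm from the device or modules.

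- **Section 9.1.5** defines malfunction: "A device malfunction is any failure of a device" "to meet its performance specifications or otherwise perform as intended". It then ties intended performance to the labeled or marketed use.
- **Section 9.3** has the investigator classify every adverse event as related or unrelated "by determining if there is a reasonable possibility that the adverse event may have been caused" by the study device. Section 9.1.4 defines an adverse device effect in similar terms, by possible causation or contribution.
- **Section 11.4** includes among its success criteria "No SAE or ADE related to the use of ATM / WST or BAM". The absence of critical module errors is a separate criterion in the same list.

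**The concern.** The main route by which the investigational component could cause harm is its advice. Under section 5.2.2, participants receive insulin settings derived from the WIT each week and are asked to enter them on their pumps. Section 5.2.2 provides for clinician evaluation when a participant raises a concern. A recommendation can come out exactly as the algorithm was written and still contribute to severe hypoglycemia or DKA. That would be module-related harm without a malfunction.

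The restart condition does not ask about that kind of harm. Severe hypoglycemia and DKA are also the events that make up the primary outcome (section 2.6). So at the moment when the study has stopped for those events, the written test for going on leaves out the question that the trial was set up to answer. No text requires relatedness to ATM/WST or BAM to be considered before resumption.

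**Working it through.** The point concerns wording, so the check is to follow one type of event through each rule.

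**Test case.** A participant enters the weekly settings as advised. ATM has computed them as specified, and the pump and CGM work normally. Severe hypoglycemia meeting section 9.2.1 follows, and the investigator judges it related to the module.

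| Rule | Question asked | Result |
|---|---|---|
| 9.2 | Reportable? | Yes |
| 9.1.4 | Possibly caused or contributed to by the device? | Yes, an adverse device effect |
| 9.3 | Reasonable possibility of causation? | Related |
| 11.4, errors criterion | Critical module error? | None, criterion met |
| 11.4, harm criterion | Module-related SAE or ADE? | Yes, criterion failed |
| 9.9.2, stop | Counts towards three? | Yes |
| 9.9.2, resume | Unrelated to an unanticipated system malfunction? | Yes, condition met |

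Three such events stop the study and then satisfy the condition for restarting it. The two rows for 11.4 show that the protocol itself separates module errors from module-related harm. The restart condition follows only the first of these.

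**How wide is the term used in 9.9.2?** The protocol defines device malfunction but not system malfunction. Section 9.8 illustrates a component malfunction with the pump, CGM and control algorithm, and its examples do not include the modules. The qualifier in 9.9.2 narrows the term further: read literally, events caused by an anticipated malfunction would also meet the restart condition.

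**The hyperglycemia reference.** Section 9.2.1 defines severe hypoglycemia. Section 9.2.2 gives four reportability criteria for hyperglycemia, one of which is DKA, and then a definition of DKA. Nothing in 9.2 is called severe hyperglycemia. The malfunction trigger could therefore mean DKA alone or any of the four.

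**Context: how often would the restart rule be used?** The exposure figures in section 11.2 reproduce: 30 × 6 = 180 participant-weeks for ATM and 15 × 6 = 90 for BAM. In years, 180 / 52 = 3.46. The documents give no event rate, so the rates below are assumptions. With m = rate × 3.46 and a Poisson count, the chance of three or more events of one type is 1 − e^(−m)(1 + m + m²/2).

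| Assumed rate per participant-year | m | Chance of ≥3 events |
|---|---|---|
| 0.05 | 0.173 | 0.08% |
| 0.1 | 0.346 | 0.5% |
| 0.2 | 0.692 | 3.3% |
| 0.5 | 1.731 | 25% |
| 1.0 | 3.462 | 67% |

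This does not prove the point. It shows that if the background rate is low, reaching three events would be unusual, so what the review has to rule out before restarting matters.

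**The case against.** There is a good deal to be said for the plan as written.

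- **The stop ignores cause.** A reader might infer that harm from a module working as designed falls outside the stopping rule. It does not: such events count towards three and stop the study. Only the restart test is open.
- **Restarting is permitted, not required.** It follows a medical and safety review, which can keep the study stopped. Meeting the condition is not automatic clearance. This stands, but malfunction is the only criterion given to that review.
- **Failing 11.4 and continuing is not a contradiction.** A reader might infer that the stopping rule and the success criteria give conflicting answers. They answer different questions: 11.4 judges the pilot when it is over, and 9.9.2 governs its conduct. A single related ADE already fails 11.4 without stopping anything.
- **The relatedness judgement already exists.** Section 9.3 yields one for each event, and 11.4 tabulates SAEs by device relationship and the remaining ADEs. What is missing is the link to resumption. Sections 5.2.2, 9.8 and 9.9.1 add clinician changes to settings, sponsor investigation of unanticipated effects and discontinuation of individuals, but none of these is a study-level restart test.
- **Malfunction could be read broadly.** Harmful advice might be called a failure to perform as intended. This is arguable, but 9.1.5 ties intended performance to labeled or marketed use, which fits poorly with modules that section 8.2 calls experimental.
- **The hyperglycemia reference has a findable target.** Section 9.2.2 is the evident place to look. That makes it a labeling point, separate from the main one.

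Nor should three events be turned into a share of the 30 participants. The rule counts events, and 9.9.1 discontinues a participant for a second event of one kind, so three events could come from two people.

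**Conclusion.** The concern holds for the restart condition. Section 9.9.2 states one criterion for resuming after three events, and that criterion does not test for the harm that ATM/WST or BAM could cause while working as specified. Sections 9.1.4, 9.3 and 11.4 do test for it. All of the triggering events could be judged module-related and the written condition would still be met.

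The conclusion rests on two readings: that malfunction in 9.9.2 carries the sense of 9.1.5, and that the study device in 9.3 includes the WIT modules, as the synopsis implies by naming the WIT as the investigational device. It does not depend on any assumed event rate. It is a defect in a stated study-level safety rule and should be corrected. It does not show that the study lacks a stop, or that reviewers would be obliged to restart. The hyperglycemia reference is a lesser wording point.

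**What to change.** Reconcile the resume condition in 9.9.2 with the relatedness assessment in 9.3 and the criteria in 11.4. The post-stop review should use and record the existing 9.3 judgement for each triggering event, stated separately for ATM/WST and for BAM. The text should say how that judgement bears on resumption and what is meant by a system malfunction. Reconcile the severe hyperglycemia reference in the suspension trigger with the event classes in 9.2.2.

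The clinical content of these rules is for the sponsor and its medical reviewers. The cost is a protocol wording amendment, which needs IRB approval under section 13.2. It adds no participants, visits or data collection, because 9.3 already requires the judgement.

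### Section 10.2 lets the study team decide whether a withdrawn participant's data are analysed; after randomisation this contradicts the all-randomised rule in 11.4 and 11.7

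*Combined protocol and SAP*

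**What the plan says.** Section 10.2 (Participant Withdrawal) notes that participation is voluntary and can end at any time. It then says that, for those who withdraw, "the study team will determine if their data will be used in" the analysis. It names no criteria and no time by which the decision is made, and it does not separate withdrawal before randomisation from withdrawal after it, or safety data from CGM data.

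Chapter 11 states a different rule in three places:

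- Section 11.4 (Safety Analyses): "All randomized participants will be included in these analyses and the circumstances of all" "reportable cases of the following will be summarized and tabulated by treatment group".
- Section 11.5 (Baseline Descriptive Statistics): "Baseline demographic and clinical characteristics of the cohort of all randomized participants will" be tabulated.
- Section 11.7 (Analysis of Secondary CGM-based Outcomes) commits to intention-to-treat, with every randomised participant in the primary safety analysis and the secondary CGM analyses.

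Section 11.7 also gives its reason for preferring a mixed model to repeated measures ANOVA: mixed "models handle missing data better (e.g. ANOVA only uses listwise deletion, which could reduce" power and bias the result towards those who complete.

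Three other sections bear on the point. Section 4.2 counts a person as enrolled from consent. Section 6.2.1 allows dropouts to be replaced. Section 6.10 asks those who withdraw to complete the final and post-study requirements.

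**The concern.** For a participant who withdraws after randomisation, inclusion is optional in Chapter 10 and mandatory in Chapter 11. Neither chapter refers to the other. Section 10.2 is the more specific rule for withdrawn participants and Chapter 11 the more specific rule for analysis, so two analysts could follow the document faithfully and build different datasets.

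Nothing keeps the decision blind to group or to results. The study team reviews uploaded device data at the weekly check-ins (6.4), and the trial is small enough for one exclusion to matter. Leaving out a withdrawn participant's whole record is the deletion that 11.7 set out to avoid, and a mixed model cannot use a record that has been taken out of the dataset. At stake are the secondary CGM comparisons and the denominators of the safety tables.

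**Working it through.** **1. The texts side by side**

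| Time of withdrawal | Section 10.2 | Sections 11.4 and 11.7 | Conflict? |
|---|---|---|---|
| After consent, before randomisation | Study team decides | Do not apply (not randomised) | No |
| After randomisation | Study team decides | Must be included | Yes |

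The harmless reading of 10.2 is the first row. The text is not limited to it.

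**2. The plan's own figures**

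Section 11.2 gives about 180 participant-weeks for the ATM and up to 90 for the BAM. These reproduce: 30 × 6 = 180 and 15 × 6 = 90. Both count every randomised participant for the full 6 weeks. Each participant wholly left out removes up to 6 weeks (180 − 6 = 174 for one), before any replacement.

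**3. Shift in a mean**

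Inputs: 30 randomised (11.2), taken as 15 per group. The SD of 11 is an assumption: 11.4 gives "Percent time in the range 70-180 mg/dL: mean 71"% ± 11 without saying what the 11 is. The documents give no withdrawal rate.

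If *k* of *n* participants, each *d* points below the mean, are left out, the mean rises by *kd*/(*n* − *k*). With *k* = 1:

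| *n* | *d* = 11 (1 SD) | *d* = 22 (2 SD) |
|---|---|---|
| 30 | 11/29 = 0.38 | 22/29 = 0.76 |
| 15 | 11/14 = 0.79 | 22/14 = 1.57 |

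For scale, the standard error of a mean is 11/√30 = 2.0 points for 30 and 11/√15 = 2.8 points for 15.

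These shifts need the participant to have data in the analysed window. Someone who left before the last two weeks adds nothing to a simple final-window mean, whether or not 10.2 is used to exclude them.

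**4. When final-window data are missing**

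Here the question is whether keeping the baseline record helps. A simulation took a group of 15, SD 11, a true change of zero, two participants without final data, and an assumed baseline-to-final correlation of 0.5, 0.7 or 0.9. The likelihood estimate included a time effect.

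- If the two with the lowest *baseline* values lack final data, leaving them out biases the mean change by about −1.3, −0.8 and −0.3 points. Keeping their baseline records gives about 0.
- If the two with the lowest *final* values are the ones missing, keeping their baseline records leaves a bias of about 2.0 points at correlation 0.5, falling to about 0.6 at 0.9.

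Retaining baseline records therefore removes the bias only when withdrawal depends on observed data and the model has a time effect. The factors that 11.7 names are subject, group, age and HbA1c; it does not name time.

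**The case against.** The strongest reply is that Chapter 11 is the analysis chapter, that it states the all-randomised rule more than once, and that a sensible reader would let it govern. The trial is also a single-site pilot with a convenience sample, its CGM comparisons are secondary, and one exclusion from 30 moves the mean by less than half a standard error. The point about size stands. The point about precedence does not, because no text gives Chapter 11 priority.

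Four stronger readings are tempting, and the documents do not support them:

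- **That a safety event could be made to disappear.** Under the criterion "No SAE or ADE related to the use of ATM / WST or BAM", dropping one participant with the only related event would turn 1/30 into 0/29. But 9.2.2 requires every reportable event to be recorded, and 11.4 requires all reportable cases to be tabulated. Section 10.2 lacks a safety exemption, yet safety is largely protected elsewhere.
- **That exclusions will follow outcome.** Section 9.6 foresees a participant being withdrawn because of an adverse event, whereas 10.2 concerns participants who themselves withdraw. The documents do not show that 10.2 reaches the first case. They fail to prevent outcome-related exclusion; they do not predict it.
- **That the CGM success criteria contradict 10.2 outright.** Criteria such as "Percent time <70 mg/dL: median <5"% state no population or time window. The all-randomised rule reaches them only because they sit in 11.4.
- **That the shifts are large.** Two of 15 left out at 2 SD below the mean would move that group's mean by 44/13 = 3.4 points. Under a normal distribution with SD 11, even removing the lowest two of 15 reaches that in only about 9% of samples.

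**Conclusion.** The contradiction is real and needs no calculation to establish. For participants who withdraw after randomisation, 10.2 conflicts with the safety analyses of 11.4 and with the intention-to-treat CGM analyses of 11.7, and it permits the completer bias that 11.7 meant to avoid. Before randomisation there is no conflict.

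The size is modest and conditional: 0.4 to 0.8 points in the mean of 30, or 0.8 to 1.6 points in a group of 15, per participant left out. This rests on 11 being a between-participant SD, on the participant lying 1 to 2 SD below the mean, and on data being present in the analysed window. The point should be fixed because a stated rule contradicts the stated analysis set and removing it costs almost nothing. It is not evidence that the results will be distorted.

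**What to change.** Limit the discretion in 10.2 to participants who withdraw before randomisation. Add to 10.2 that every randomised participant, including one who is later replaced, is analysed in the assigned group with all data collected: baseline CGM, any on-treatment CGM and all safety data. Put a cross-reference in 6.2.1, so that replacement is not read as removal.

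The amended text should not claim that keeping baseline records removes bias from withdrawal. The gain is an analysis set fixed in advance and no longer open to choice once results are visible.

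The cost is a wording amendment with IRB approval (13.2). No visit or measurement is added, since 6.10 already asks for final data from those who withdraw. The study team gives up the option to exclude a randomised participant who withdraws.
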